13.4. VITAL SIGNS

The following vital signs measurements will be reported for this study:

- Systolic Blood Pressure (mmHg)
- Diastolic Blood Pressure (mmHg)
- Pulse Rate (bpm)
- Temperature (°C)
- Weight (kg)
- Height or length (cm)
- Head circumference (cm) for subjects ≤ 36 months of age

The following vital signs parameters will be derived for this study:

Document: T:\Shire\Teduglutide\XXA39799\Biostatistics\Documentation\SAP\SHP633-302 SAP Final

1.0_17Apr2019.docx

Author: Version Number: Final 1.0 Version Date: 17Apr2019

Template No: CS_TP_BS016 Revision 4 Reference: CS_WI_BS005

Effective Date: 01Apr2016

- BMI (kg/m2) for children 2-15 years of age
- Weight for length ratio (kg/cm) for infants 4-<12 months corrected gestational age
- Height or length for age Z-score
- Weight for age Z-score
- BMI for age Z-score for children 2-15 years of age
- Weight for length Z-score for infants 4-<12 months corrected gestational age
- Head circumference for age Z-score for subjects ≤ 36 months of age

Descriptive statistics (e.g., mean, standard deviation, median, minimum and maximum values, the number and percent of subjects in specified categories) will be used to summarize the vital signs at each scheduled study site visit and at EOT. Both observed value and change from baseline will be summarized with descriptive statistics defined in Section 6.1. Mean \pm SE plots of body weight, height or length, BMI and head circumference for age Z-scores and weight for length Z-score by visit will be generated.

The following specific derivations will be used:

BMI

BMI = 10000* Body weight (kg)/body height (cm)², where both body weight and body height data are available at the same scheduled visit. BMI will only be presented for Children 2-15 years of age.

Weight for length ratio

Weight for length ratio = Body weight (kg)/length (cm), where both body weight and length data are available at the same scheduled visit. Weight for length ratio will only be presented for the infant cohort.

 Height or length, Weight, Head Circumference, BMI for age Z-scores and weight for length Zscore

A z-score is the deviation of the value for an individual from the mean value of the reference population divided by the standard deviation for the reference population.

Z-scores are calculated using the formula below:

Z-score= $[((observed value / M) ^ L) - 1] / (S * L), for L \neq 0$

Z-score= In(observed value / M) / S, for L=0

In which 'observed value' is the child's height or length, weight, head circumference or derived BMI. The L, M, and S values vary according to the child's sex, age or length. The following data tables containing the L, M and S values for child's height or length, weight, head circumference, derived BMI for age and weight for length will be used.

Document: T:\Shire\Teduglutide\XXA39799\Biostatistics\Documentation\SAP\SHP633-302 SAP Final

1.0 17Apr2019.docx

Template No: CS_TP_BS016 Revision 4

Effective Date: 01Apr2016

Author:

Version Date: 17Apr2019

Version Number:

Reference: CS_WI_BS005

Final 1.0

Reference: CS WI BS005

	Height or Length		Weig	Weight		Weight for Length [4]	Head Circumference	
Age	Children 1-15 yrs [1]	Infants 4-<12 mos [2]	Children 1-15 yrs [1]	Infants 4-<12 mos [2]	Children 1-15 yrs [1]	Infants 4-<12 mos [2]	Children 1-15 yrs [1]	Infants 4-<12 mos [2]
0- <12 mos	NA	WHO	NA	WHO	NA	WHO	NA	Kato 2014
1-<2 yrs	Isojima 2016	WHO	Isojima 2016	WHO	NA	WHO	Kato 2014	Kato 2014
2-3 yrs	Isojima 2016	NA	Isojima 2016	NA	Kato 2011	NA	Kato 2014	NA
>3 yrs	Isojima 2016	NA	Isojima 2016	NA	Kato 2011	NA	NA	NA

- [1] Actual (chronological) age at the time of assessment is used for Z-score calculation.
- [2] Corrected gestational age at the time of assessment is used for Z-score calculation.
- [3] BMI is only calculated for Children 2-15 years of age.
- [4] Weight for length is only calculated for the cohort of infants.

NA = Not applicable; mos = Months; yrs = Years

To obtain the L, M, and S values using these data tables, the corrected gestational age will be used for infants and the actual (chronological) age for children 1-15 years of age. Note that the calculated age at each vital sign assessment date will be obtained using the date of birth as reference date for actual (chronological) age and (date of birth + difference in days between corrected gestational age and actual age at informed consent) as reference date for corrected gestational age.

Details of the Z-score calculation are provided in subsections below.

Z-scores will be rounded to 2 decimal places for reporting.

For more information on the LMS method, see

http://www.ncbi.nlm.nih.gov/pmc/articles/PMC27365/.

Official and validated SAS programs created by Centers for Disease Control and Prevention (CDC) will be used to calculate the Z-scores for a child's sex and age (up to 20 years of age) for BMI, weight, height, and head circumference based on the L, M, S values referred above. For more information on the CDC SAS programs, see http://www.cdc.gov/growthcharts/computer_programs.htm.

Document: T:\Shire\Teduglutide\XXA39799\Biostatistics\Documentation\SAP\SHP633-302 SAP Final

1.0_17Apr2019.docx

Author: Version Number: Final 1.0 Version Date: 17Apr2019

Template No: CS_TP_BS016 Revision 4

Effective Date: 01Apr2016

Copyright © IQVIA. All rights reserved.

13.4.1. Z-SCORES OF HEIGHT FOR AGE AND WEIGHT FOR AGE FOR CHILDREN 1-15 YEARS OF AGE

The L, M and S values of height and weight for age for Japanese children as given in Isojima et al. (2016) will be used. These values are also given in Table 1 (for height) and Table 2 (for weight) of APPENDIX 2.

For ages (in years) that fall between two age categories given in Table 1 and Table 2, the following interpolation will be used to calculate the L, M, S values:

LMS value=LMS_lower + [(actual age in years - age_lower) * (LMS_upper - LMS_lower)] / (age_upper - age_lower).

Where LMS_lower is the L, M or S value corresponding to the lower age category in the age interval, i.e., age_lower, and LMS_upper is the L, M or S value corresponding to the upper age category in the age interval, i.e., age_upper.

For example, according to Table 1 in APPENDIX 2, the M values of height are 135.9 for a 10 years old male and 138.8 for a 10.5 years old male. Therefore, to obtain the M value of height for a 10.2 years old male, the following calculation is applied:

M=135.9 + [(10.2 - 10) * (138.8 - 135.9)] / (10.5 - 10) = 137.06

13.4.2. Z-SCORES OF LENGTH FOR AGE AND WEIGHT FOR AGE FOR INFANTS **4-12** MONTHS CORRECTED GESTATIONAL AGE

L, M, S values for WHO growth charts will be used:

https://www.cdc.gov/growthcharts/who charts.htm

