- Infants: 4-<12 months corrected gestational age
- Children: 1-15 years of age

The corrected gestational age as captured on the demographics page of the eCRF will be used to determine the cohort a subject belongs to, i.e., if the corrected gestational age is <12 months, the subject will be in the infant cohort. The infant cohort will be analyzed in a manner analogous to the cohort of children 1-15 years of age unless specified otherwise.

Analyses will be done for all subjects, and subset of subjects who began treatment after protocol amendment 3.0. Main conclusions will be based on subjects who began treatment after implementation of protocol amendment 3.0.

Document: T:\Shire\Teduglutide\XXA39799\Biostatistics\Documentation\SAP\SHP633-302 SAP Final

1.0_17Apr2019.docx

Template No: CS_TP_BS016 Revision 4

Effective Date: 01Apr2016

Author:

Version Date: 17Apr2019

Version Number:

Reference: CS_WI_BS005

Final 1.0

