13.4.3. Z-SCORES OF HEAD CIRCUMFERENCE FOR ALL STUDY SUBJECTS ≤36 MONTHS OF AGE

The L, M and S values of head circumference for age for Japanese population as given in Kato et al. (2014) will be used. These values are also given in Table 5 of APPENDIX 2.

Corrected gestational age will be used for infants and the actual (chronological) age for children 1-3 years of age.

For ages (in months) that fall between two age categories given in Table 5, a similar interpolation as described in Section 13.4.1 will be used to calculate the L, M, S values.

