APPENDIX 1. MARKEDLY ABNORMAL LABORATORY CRITERIA

Lab Parameter	Unit	`	- <12 months estational age)	Children (1 - 15 years)		
		Lower Limit Criteria	Upper Limit Criteria	Lower Limit Criteria	Upper Limit Criteria	
Chemistry						
Albumin	g/L	<20	>68	<20	>68	
Alkaline Phosphatase	U/L		>5 x ULN		>5 x ULN	
Alanine Aminotransferas e (ALT)	U/L		>8 x ULN		>8 x ULN	
Aspartate Aminotransferas e (AST)	U/L		>8 x ULN		>8 x ULN	
Amylase	U/L		>3 x ULN		>3 x ULN	
Lipase	U/L		>3 x ULN		>3 x ULN	
Bilirubin Total	umol/L		>5 x ULN		>3 x ULN	
Direct Bilirubin	umol/L		>68.4147		>34.208	
Blood Urea Nitrogen	mmol/L		>12.495		>12.495	
Calcium	mmol/L	<1.5	>3	<1.5	>3	
Creatinine	umol/L)	>132.6		>132.6 if age < 10 y; >150.28 if age 10- <13 y; >176.8 if age 13-<16 y; >221 if age 16+	
C Reactive Protein	mg/L		>=100		>=100	
Glucose	mmol/L	<2.22	>13.875	<2.22	>13.875	
Magnesium	mmol/L	<0.4114	>1.2342	<0.4114	>1.2342	
Phosphorus	mmol/L	<0.644	>2.254	<0.644	>2.254	

Document: T:\Shire\Teduglutide\XXA39799\Biostatistics\Documentation\SAP\SHP633-302_SAP_Final

1.0_17Apr2019.docx Author:

Template No: CS TP BS016 Revision 4

Effective Date: 01Apr2016

Version Date: 17Apr2019

Reference: CS_WI_BS005

Final 1.0

Version Number:

Copyright © IQVIA. All rights reserved.

Potassium	mmol/L	<2.5	>6.5	<2.5	>6.5
Sodium	mmol/L	<120	>160	<120	>160
Triglycerides	mmol/L		>5.65		>5.65
Hematology					
Hemoglobin	g/L	<70	>200	<70	>200
Hematocrit	fraction of 1	<0.21	>0.60	<0.21	>0.60
Platelets	10^9/L	<75	>700	<75	>700
Leukocytes	10^9/L	<2	>30	<2	>30
Neutrophils, absolute	10^9/L	<0.5		<0.5	

1.0_17Apr2019.docx

Template No: CS_TP_BS016 Revision 4

Effective Date: 01Apr2016

Author:

Copyright © IQVIA. All rights reserved.

The contents of this document are confidential and proprietary to IQVIA. Unauthorized use, disclosure or reproduction is strictly prohibited.

Document: T:\Shire\Teduglutide\XXA39799\Biostatistics\Documentation\SAP\SHP633-302 SAP Final

Version Number: Version Date:

Final 1.0 17Apr2019

Reference: CS_WI_BS005

APPENDIX 2. L, M and S Values of Height, Body Weight, BMI and Head Circumference for Age for Japanese

Table 1 L, M and S Values of Height for Age for Japanese Children

Age (yr) -		Male			Female	
Age (y1)	L	\mathbf{M}	S	L	\mathbf{M}	S
0	2.300	49.0	0.0417	1.200	48.5	0.0390
0.25	2.212	61.5	0.0378	1.159	60.1	0.0361
0.5	2.124	67.7	0.0351	1.117	66.2	0.0341
0.75	2.036	71.6	0.0335	1.076	70.2	0.0327
1	1.948	74.8	0.0328	1.034	73.5	0.0318
1.25	1.861	77.8	0.0328	0.993	76.6	0.0316

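### Child-cohort growth Z-scores use chronological age while infants stay on corrected age past 12 months, so preterm-born children entering at 1 to <2 years get a low baseline height Z and a partly spurious gain

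*SAP*

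**What the plan says.** Section 6.1 assigns the cohort: "The corrected gestational age as captured on the demographics page of the eCRF will be used to determine the cohort a subject belongs to", and "if the corrected gestational age is <12 months, the subject will be in the infant cohort".

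Section 13.4 then fixes the age at which L, M and S are read: "the corrected gestational age will be used for infants and the actual (chronological) age for children 1-15 years of age". The reference table there repeats the rule in its notes. The child columns carry note "1] Actual (chronological) age at the time of assessment is used for Z-score calculation", and the infant columns carry note "2] Corrected gestational age at the time of assessment is used for Z-score calculation". The infant columns include a row for 1 to <2 years, so an infant-cohort subject who passes 12 months corrected during the study is still scored at corrected age. Section 13.4.3 applies the same split to head circumference: "Corrected gestational age will be used for infants and the actual (chronological) age for children 1-3 years of age".

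Section 13.4 also supplies a reference date for corrected age: the birth date shifted by the gap between corrected and actual age at consent. Observed Z-scores and changes from baseline are summarized, with mean ± SE plots, and baseline Z-scores appear in the section 9.1 demographics. The SAP gives no reason for the split and no sensitivity analysis.

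**The concern.** A preterm-born child just over 12 months corrected falls in the child cohort and is compared with a reference child who is older by the degree of prematurity. An infant-cohort subject who reaches the same corrected age during the study is not. The SAP thus accepts corrected age beyond 12 months in one cohort and not in the other, although corrected age is what separates them.

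Two things follow for such a child. Height at baseline looks lower than it is for corrected age. The deficit then shrinks as the child gets older, because early growth slows and the spread of the reference widens, so height Z rises in a child who is only tracking the median. Growth is a named safety assessment (section 2.2.2), the study is open-label with no control arm, and the false rise favours the drug. A true small loss of height Z in such a child could read as no change.

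**Working it through.** **Inputs.** L, M and S come from Appendix 2 (Table 1 height, Table 2 weight, Table 5 head circumference). Interpolation follows section 13.4.1. The score is Z = [(x/M)^L - 1]/(S × L) from section 13.4. Treatment lasts 24 weeks, 168/365.25 = 0.46 year. Degree of prematurity is not in the SAP; 4 to 16 weeks is assumed.

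**Reproduction of the SAP's own example.** M for a 10.2-year-old boy: 135.9 + (0.2 × 2.9)/0.5 = 137.06, as printed.

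**Check on tabulated rows.** The Table 1 rows are "1 1.948 74.8 0.0328 1.034 73.5 0.0318" and "1.25 1.861 77.8 0.0328 0.993 76.6 0.0316" (age, then L, M, S for boys and for girls). A child on the 1.00-year median, scored at 1.25 years (3 months preterm):
- Boy: [(74.8/77.8)^1.861 - 1]/(0.0328 × 1.861) = -1.16
- Girl: [(73.5/76.6)^0.993 - 1]/(0.0316 × 0.993) = -1.28

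**Boy 12 weeks preterm, entering at 1.02 years corrected.**
- Baseline: chronological age 1.02 + 84/365.25 = 1.25. Height = 74.8 + 0.02 × 3.0/0.25 = 75.04 cm. Scored on the 1.25-year row, Z = -1.06.
- Week 24: corrected age 1.48, median 80.47 cm. Chronological age 1.71, where L = 1.699, M = 82.97, S = 0.0339. Z = -0.88.
- Apparent gain +0.18. The girl goes from -1.18 to -0.96, a gain of +0.22.

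**Why it drifts.** In boys the median rises 3.0 cm from 1.00 to 1.25 years but 2.4 cm from 1.75 to 2.00 years. Meanwhile M × S goes from 77.8 × 0.0328 = 2.55 cm at 1.25 years to 85.8 × 0.0348 = 2.99 cm at 2 years.

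**Height Z at baseline, and change over 24 weeks (boy / girl), child on the corrected-age median.**

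| Weeks preterm | Entry 1.02 y corrected | Entry 1.5 y | Entry just under 2 y |
|---|---|---|---|
| 4 | -0.37 / -0.40; +0.06 / +0.07 | -0.30 / -0.32; +0.08 / +0.09 | -0.20 / -0.21; +0.02 / +0.03 |
| 12 | -1.06 / -1.18; +0.18 / +0.22 | -0.87 / -0.95; +0.27 / +0.31 | -0.58 / -0.61; +0.06 / +0.10 |
| 16 | -1.38 / -1.53; +0.25 / +0.29 | -1.12 / -1.22; +0.34 / +0.39 | -0.76 / -0.80; +0.07 / +0.13 |

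A finer grid of entry ages raises the largest gains by no more than about 0.02.

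**A short child.** At true Z = -2, 3 months preterm and 12 months corrected, the offset is -1.02 / -1.22 and the change +0.21 / +0.26. The effect is not peculiar to the median.

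**Head circumference, boys.** 12.5 months corrected scored at 15.5 months: [(46.2032/47.0232)^1.86419 - 1]/(0.029906 × 1.86419) = -0.58. With entry at 12 months corrected and 3 months preterm, Z goes from -0.61 to -0.33, a change of +0.28.

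**Weight.** Boys' offset is about -0.1 to -0.7 over the same range. At 12 weeks preterm and 1.02 years corrected the 24-week change is -0.01 (boy) and +0.03 (girl). The largest change found is about +0.16 (boy, 16 weeks preterm, entry at 1.5 years).

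**With corrected age.** The same child scores 0.00 at baseline and 0.00 at week 24 on every measure.

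**The case against.** The rule is explicit and stated the same way in the text, the table notes and section 13.4.3, so it is a choice rather than a slip. Calling the scores low presupposes that corrected age remains the right basis after 12 months. The SAP may keep infants on it only so that each subject has a single basis throughout. That stands in part. The SAP's own use of corrected age up to <2 years for infants is still the internal precedent, and no reason is given for treating child-cohort subjects of the same age differently.

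The cohorts are tabulated separately, and infants use WHO height and weight references while children use Japanese ones. Some difference between cohorts would therefore remain under any age rule. This is right, and it makes the drift within the child cohort the more important part.

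The consequence is also limited. Raw height and weight are summarized as well. The PK Analysis Plan (section 5) gives a minimum of 5 children. If one of five were a girl 12 weeks preterm entering at 1.02 years, the mean baseline height Z would move by -1.18/5 = -0.24 and the mean change by 0.22/5 = +0.04. The real number of such children is unknown.

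A reader might infer that preterm-born toddlers in general are scored about 1 SD too low. The documents do not support that: it needs roughly 12 weeks of prematurity and entry at about 12 to 18 months corrected. A reader might also infer that a child's age basis switches during the study. It does not; the break lies between cohorts.

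**Conclusion.** The inconsistency is real and its direction is clear. For entry at 1 to <2 years corrected, the baseline height Z offset runs from about -0.2 (4 weeks preterm, near 2 years) to -1.5 (16 weeks, near 1 year). The spurious 24-week gain runs from +0.02 to +0.39. The gain recovers only part of the offset. Head circumference behaves similarly in the boys' cases worked. Weight Z is offset, but its change is near zero for entry near 12 months.

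These sizes assume a child tracking the corrected-age median and a degree of prematurity that the SAP does not give. Whether any enrolled child is affected cannot be told from the document. Only descriptive growth safety and baseline summaries are touched. No efficacy endpoint uses these Z-scores, and a reading that the efficacy results are biased would have no support. The change is worth making because it is cheap and the artefact is favourable to the drug in a small uncontrolled cohort.

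**What to change.** In sections 13.4 and 13.4.3, and in note [1] of the table, state that child-cohort subjects below 24 months corrected age at baseline have L, M and S looked up at corrected age at all visits. This covers height, weight, head circumference and any BMI Z-score that becomes due, so that one child's measures share one basis. Use the reference-date derivation already in 13.4, and chronological age for all other child-cohort subjects. The 24-month limit matches where the table's corrected-age rows end.

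The cost is a wording change and one condition in the age derivation, since corrected age is already taken from the eCRF to assign cohort. The downside is a smaller break at 24 months, about -0.6 SD in height at 12 weeks preterm (-0.57 boy, -0.60 girl), which should be footnoted. The WHO and Japanese references still differ between cohorts.

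If the sponsor keeps chronological age as the main display, give the reason and present corrected-age Z-scores for these subjects as a sensitivity display.

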13.4.3. Z-SCORES OF HEAD CIRCUMFERENCE FOR ALL STUDY SUBJECTS ≤36 MONTHS OF AGE

The L, M and S values of head circumference for age for Japanese population as given in Kato et al. (2014) will be used. These values are also given in Table 5 of APPENDIX 2.

Corrected gestational age will be used for infants and the actual (chronological) age for children 1-3 years of age.

For ages (in months) that fall between two age categories given in Table 5, a similar interpolation as described in Section 13.4.1 will be used to calculate the L, M, S values.

13.4.4. Z-SCORES OF BMI FOR CHILDREN 2-15 YEARS OF AGE

The L, M and S values of BMI for age for Japanese children as given in Kato et al. (2011) will be used. These values are also given in Table 3 (for male) and Table 4 (for female) of APPENDIX 2. BMI for age Z-scores will only be presented for the children 2-15 years of age.

Document: T:\Shire\Teduglutide\XXA39799\Biostatistics\Documentation\SAP\SHP633-302 SAP Final

1.0 17Apr2019.docx

Author: Version Number: Final 1.0 Version Date: 17Apr2019

Template No: CS TP BS016 Revision 4 Reference: CS WI BS005

Effective Date: 01Apr2016

13.4.5. Z-SCORES OF WEIGHT FOR LENGTH FOR INFANTS

L, M, S values for WHO growth charts will be used:

https://www.cdc.gov/growthcharts/who charts.htm

Weight for length Z-scores will only be presented for the infant cohort.

13.5. ECG VARIABLES

The number and percentage of subjects with each type of ECG finding (Normal/Abnormal, Not Clinically Significant/Abnormal, Clinically Significant) will be presented at baseline, weeks 12, 24 and 28 as well as at EOT for the Safety population.

13.6. Physical Examination

Physical exam findings will be presented in the listings for the Safety population.

13.7. ANTIBODIES TO TEDUGLUTIDE

A summary table will provide the number of subjects with a sample analyzed for baseline, Week 24, EOT and Week 28. The summary table will also provide the number of subjects with an antibody finding (Antibodies to teduglutide Negative/Positive and No Neutralizing Antibodies Present/Neutralizing Antibodies Present) at each of those visits.

13.8. GASTROINTESTINAL-SPECIFIC TESTING

The results of GI-specific testing including UGI/SBFT, abdominal ultrasound, fecal occult blood testing, and colonoscopy/ sigmoidoscopy will be reported as 'Normal', 'Abnormal, not clinically significant', 'Abnormal, clinically significant' or 'Negative', 'Positive, not clinically significant', 'Positive, clinically significant'. For the infant cohort, only UGI/SBFT is to be reported. The number of patients and percentage will be presented by visit for each GI-specific testing parameter and result category.

13.9. FECAL AND URINE OUTPUT

Output diary data is recorded over a 48 hour period of PN/IV and EN stability before every scheduled site visit and within 1 week of implementing any PN/IV prescription adjustment. For

Document: T:\Shire\Teduglutide\XXA39799\Biostatistics\Documentation\SAP\SHP633-302 SAP Final

1.0_17Apr2019.docx

Version Number: Final 1.0 Version Date: 17Apr2019

Reference: CS WI BS005

Template No: CS TP BS016 Revision 4

Effective Date: 01Apr2016

Author:

Copyright © IQVIA. All rights reserved.

the analysis, the latest 48-hour period of output diary data entered prior to each visit will be used (The 48-hour period does not need to be within 48 hours of the visit). Any additional output diary data collected out of this 48-hour window will only be presented in the listings.

The average daily urine output (mL/kg/day) at the scheduled site visit will be calculated as follows:

(Total urine output over 48 hours / 2) / most recent body weight (kg) prior to or on the scheduled visit

where total urine output is calculated as the sum of the urine output in mL and the urine-only diaper weights in g (1g = 1mL) for the subject collected on the output diary form of eCRF over 48 hours. Values will not be calculated if the urine output is not available at the visit.

The average daily fecal output will be summarized separately by the number of stools per day, the typical stool form score using Bristol Stool Form Scale, the total daily stool/mixed stool diaper weight (g/kg/day) and the total ostomy output per day (mL/kg/day). The number of stools per day and the average typical stool form score will be calculated as (sum of the daily data in a 48-hour period / 2). The body weight will be used to calculate the daily stool/mixed stool diaper weight (g/kg/day) and the total ostomy output per day (mL/kg/day) using a formula analogous to that used to calculate the average daily urine output.

The change and the percent change in average daily output for urine and fecal from baseline to each scheduled visit, as well as at EOT, will be presented using descriptive statistics defined in Section 6.1.

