6.3. HANDLING OF DROPOUTS OR MISSING DATA

All subjects in the analysis population defined in Section 7 will be included in the associated analyses.

No imputation for missing data (e.g., last observation carried forward [LOCF]) will be applied except for the partial dates for adverse events and prior/concomitant medications.

Details on how to handle partial dates for adverse events and prior/concomitant medications are described below.

Complete dates will be imputed from partial dates of adverse events and medications solely for the purpose of defining treatment emergence for adverse events and prior/concomitant status for medications (Imputed dates will not be presented in the listings). Dates will be defined using the hierarchy of derivations below.

Adverse event or medication start date (references to month and year are the month and year of the start date):

- 1. If year and month are known, and it is the month and year of the first dose date, use the first dose date.
- 2. If year and month are known, and it is not the month and year of the first dose date, use the first day of the month.
- 3. If only year is known, and it is the year of the first dose date, use the first dose date.
- 4. If only year is known, and it is not the year of the first dose date, use the first day of the year (1st January).
- 5. Should any of the previous start dates created be after a complete stop date provided, use the stop date as the start date, instead of the date that would otherwise be created.
- 6. For medication start date, if "Before Informed Consent" is ticked then use the date of informed consent.
- 7. Otherwise, if start date is unknown leave as missing.

Adverse event or Medication stop date (references to month and year are the month and year of the stop date):

Document: T:\Shire\Teduglutide\XXA39799\Biostatistics\Documentation\SAP\SHP633-302 SAP Final

1.0 17Apr2019.docx

Version Number: Version Date: Final 1.0 17Apr2019

Reference: CS WI BS005

Author:

Template No: CS TP BS016 Revision 4

Effective Date: 01Apr2016

- 1. If year and month are known, use the last day of the month.
- 2. If only year is known, use the last day of the year (31st December).
- 3. Otherwise, if stop date is unknown leave as missing.

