11. EFFICACY/PHARMACODYNAMIC EVALUATION

11.1. Analysis of Efficacy and Pharmacodynamic Variables

Primary efficacy/pharmacodynamic analyses will be conducted on the ITT population. The PP population will be used for sensitivity analysis purpose.

PN/IV and EN support will be reported in both subject diary data and the investigator-prescribed data in the eCRF. Diary and prescribed PN/IV and EN volume/calories will be normalized to weight in order to facilitate comparability of results across patients in this pediatric population. Data will be summarized at all scheduled visits during the 24-week treatment period and the follow-up period (Week 25, 26, 27, 28). An End of Treatment (EOT) time point will also be added. Data collected at unscheduled time points will be included in the listings but will not be summarized at those unscheduled time points.

Prescribed data are the most recent PN/IV or EN prescription (from either baseline or prescription adjustments) prior to or on the date of visit, captured in the PN/IV or EN history and PN/IV or EN adjustments eCRFs.

Average daily values normalized to weight will be calculated for PN/IV volume, PN/IV calories, EN volume and EN calories as follows:

Average Prescribed daily value = (prescribed weekly value / 7) / last available body weight prior to or on the date of visit

Calculation of post-baseline diary PN/IV and EN parameters (including hours per day and days per week of PN/IV support) will be based on the daily support recorded in subjects' diaries within 7 days prior to the date of each scheduled post-baseline visit. Baseline diary PN/IV and EN parameters will be calculated using the most recent 14 days of diary data collected prior to the first dose, and week 1 calculations will not use any pre-baseline diary data.

Average daily values normalized to weight will be calculated for PN/IV volume, PN/IV calories, EN volume and EN calories as follows:

Average diary daily value = (sum of non-missing daily values in the diary / number of days with non-missing values) / last available body weight prior to the visit

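### SAP Section 13.9 divides the stool form score by 2 even when only one day has a score, and sets no earliest date for the 48-hour period used at a visit

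*SAP*

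**What the plan says.** SAP Section 13.9 describes the collection as follows: "Output diary data is recorded over a 48 hour period of PN/IV and EN stability before every scheduled site visit", with a further collection around PN/IV prescription adjustments. For analysis, "the latest 48-hour period of output diary data entered prior to each visit will be used", and a parenthesis adds: "The 48-hour period does not need to be within 48 hours of the visit". No earliest date is given.

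The divisor is 2 throughout the section:

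- Stool count and form score share one formula: "the average typical stool form score will be calculated as (sum of the daily data in a 48-hour period / 2").
- Urine is "Total urine output over 48 hours / 2) / most recent body weight (kg) prior to or on the scheduled visit".
- Diaper weight and ostomy output are derived "using a formula analogous to that used to calculate the average daily urine output".

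The section has one missing-data guard: no urine value is derived where urine output is unavailable at the visit. It does not define unavailable, does not address a period with one recorded day, and does not state the guard for stool count or form score. Change and percent change from baseline are then summarised by visit.

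Elsewhere, Section 6.3 says "No imputation for missing data (e.g., last observation carried forward [LOCF]) will be applied", apart from partial dates. For the PN/IV and EN diaries, Section 11.1 uses "sum of non-missing daily values in the diary / number of days with non-missing values", with a limit on missing days, and keeps pre-baseline diary data out of the Week 1 calculation.

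**The concern.** Dividing a 48-hour total by 2 is the right conversion for a quantity such as urine volume or number of stools. It is wrong for a rating. A day without a stool contributes nothing to rate, so the sum holds one score while the divisor still counts two days. The result is not an average of anything observed, and can fall below the lowest score on the scale. No data need be missing for this to happen.

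The open look-back raises a second problem. If no new collection was made before a visit, the latest period entered is the one from the previous collection. Applied literally, the rule tabulates that period as the current visit's result, and the summary would not show that it had been used before.

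Urine and fecal output are listed safety assessments (SAP Section 2.2.2). The PK analysis plan (Section 5) gives planned minimum enrolment as 5 children and 2 infants, so a single wrong value visibly moves a by-visit mean.

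**Working it through.** The documents give no figure to reproduce on this point, so the formulas are applied to example diaries.

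**Inputs.** From the documents: the divisor of 2 (Section 13.9); the days-with-data divisor (Section 11.1, for comparison); summarised site visits at baseline and Weeks 1, 2, 4, 6, 8, 10, 12, 15, 18, 21, 24 and 28 (Section 13.3). Assumed for illustration: the daily values, a scale running from 1 to 7, and no score on a day without a stool.

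**Form score.** SAP rule: sum of scores / 2. Alternative: sum of scores / number of scored days.

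| Scores on the two days | SAP rule | Mean over scored days |
|---|---|---|
| 6 and 6 | 12/2 = 6.0 | 12/2 = 6.0 |
| 6 and none | 6/2 = 3.0 | 6/1 = 6.0 |
| 7 and none | 7/2 = 3.5 | 7/1 = 7.0 |
| 1 and none | 1/2 = 0.5 | 1/1 = 1.0 |

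The two rules agree when both days are scored. When one is not, the SAP rule gives exactly half. The value 0.5 lies below the assumed scale minimum.

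**Percent change when stool form has not changed (6 on every scored day).**

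- Both days scored at baseline, one at the visit: (3 − 6)/6 = −50%.
- One day scored at baseline, both at the visit: (6 − 3)/3 = +100%.

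**Effect on a cohort mean.** One score of 6 reported as 3 is an error of 3 points. With 5 children the mean moves by 3/5 = 0.6; with 2 infants it moves by 3/2 = 1.5.

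**Stool count, as a contrast.** Counts of 5 and a recorded 0 give (5 + 0)/2 = 2.5, which is correct. Only an unrecorded day would make 5/2 = 2.5 wrong.

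**Look-back.** Successive summarised site visits are 1, 1, 2, 2, 2, 2, 2, 3, 3, 3, 3 and 4 weeks apart. A missed collection can therefore bring in data from about one visit interval earlier, or more if several are missed, unless a collection around a prescription adjustment falls in between. At Week 1 the latest period may be the baseline one. Stool count and form score are not divided by weight, so their change from baseline is then 0 by construction. Section 11.1 closes this route for the PN/IV and EN diaries; Section 13.9 does not close it for output.

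**The case against.** The strongest reply is that Section 13.9 describes a fixed 48-hour collection, for which dividing by 2 is the natural daily conversion. One recorded day can fairly be read as not being a 48-hour period at all, and counting a blank day as zero would itself be imputation, which Section 6.3 bars. The PN/IV diary rule concerns 7 or 14 daily entries, so a different divisor there is not in itself a contradiction. On the look-back, collection is planned before every site visit, the parenthesis relaxes only the closeness to the visit, and the general no-LOCF rule already argues against reuse.

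Much of this stands, and it rules out several stronger readings that a reader might infer:

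- That the plan treats every unrecorded day as zero for urine, ostomy and diaper weight. The text does not say so; it leaves incomplete periods unaddressed.
- That a missed urine collection silently reuses old data. The urine guard makes that an unlikely reading, and the guard arguably extends to the measures derived by analogy with urine.
- That stool-free days understate stool count or stool weight. A true zero is handled correctly there.
- That the error always favours firmer stool or lower output. It reverses when the single-score day falls at baseline.

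The reply does not rescue the form score. A complete two-day diary with one stool-free day satisfies the 48-hour reading, needs no imputation, and is still halved. Nor does it supply an earliest date or a guard for stool count and form score. Someone programming the specific rule in Section 13.9 would not necessarily recognise it as the carry-forward that Section 6.3 excludes.

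**Conclusion.** The form-score formula gives a wrong result under ordinary, complete data: half the true value whenever exactly one of the two days has a score. This rests only on a stool-free day carrying no score; the output diary form is not shown. The off-scale example also assumes a 1 to 7 range, which the SAP does not state.

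The look-back is a gap in wording. Read literally, it permits reuse of an earlier period for stool count and form score, and so conflicts in effect with Section 6.3. It does not show that reuse is intended.

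The documents do not say how often stool-free days or missed collections occur, so the total effect cannot be estimated. The consequence is confined to descriptive safety summaries; no efficacy endpoint uses these values and the SAP makes no inferential claims. It should be corrected because the fix is nearly free, but it does not threaten the main conclusions.

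**What to change.** Amend Section 13.9 as follows:

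1. Average the stool form score over the days in the 48-hour period that have a recorded score; set it to missing if there is none.
2. For stool count, diaper weight, ostomy output and urine, set the value to missing unless both days are recorded. A recorded day with no stool counts as zero.
3. Require the 48-hour period for a visit to fall after the previous scheduled site visit and, for post-baseline visits, after the first dose.
4. Define when output is unavailable at a visit, and apply that rule to all output measures.

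This takes a few sentences and a small programming change. The cost is slightly more missing by-visit values. Form scores with both days scored, and counts, weights and volumes with both days recorded, are unchanged where the collection falls in the permitted interval.
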